## 1.0 Objectives

### 1.1 Study Objectives

Advance care planning (**ACP**) is the process of thinking through and articulating in advance one's preferences for future medical care. It has long been promoted as a way for people to receive medical treatment consistent with their values, goals, and preferences. While ACP typically involves decision-making about specific life sustaining treatments, choosing *who* will make medical decisions when the patient cannot is considered by many to be the single most important ACP action a person can take. When patients fail to designate a healthcare spokesperson (henceforth **spokesperson**), it leads to uncertainty about who will make medical decisions, what treatments are to be accepted or declined, and on what basis—which can lead to familial conflict, unwanted and costly medical care, and avoidable patient suffering. So, too, when patients choose the “wrong” person to represent them, their wishes are less likely to be known or respected. Our own research suggests that when patients prefer fewer aggressive medical treatments, there is significantly lower concordance between spokespersons' decisions and patients' wishes.

Patients, families, and ACP experts have identified several qualities as being especially important for spokespersons to have. Ideally, they should know the patient's values, be available when needed, be trustworthy and caring, have good judgment, and be able to stand up under pressure. That said, many individuals (and state laws) assign spokespersons on the basis of relationship (spouse, parent, etc.) rather than personal qualities. Surprisingly, no interventions (to our knowledge) are explicitly designed to help people consider the *actual* qualities of the person they choose, much less *engage* this individual to confirm they can fully represent the patient's wishes should the need arise.

To address these gaps, we have developed a novel intervention that includes a “serious game” to help people consider the qualities they want in their spokesperson, then engage the person they choose for this role. Combining a serious topic with an enjoyable activity (“gamification”) has been effective at changing health related behaviors in multiple settings with our target population (“sandwich generation” and older adults). The game element of our intervention, “*Who Would You Choose: Serious Fun*” (**WWYC**), prompts players (using scenarios and metaphors) to choose a spokesperson whose qualities are best suited to the role. At the end of the game, players identify a real-life spokesperson based on the qualities considered during gameplay. Then, using an online interface, WWYC will spark communication between the player and their chosen spokesperson. The long-term goal of this project is to help people make more thoughtful and informed choices when selecting a spokesperson, and to help these spokespersons be better prepared for their role as surrogate decision-makers. The current mixed methods study proposed here is designed to learn whether and how WWYC helps individuals select an appropriate spokesperson for healthcare decisions, as assessed via three **Specific Aims**:

**Aim 1 (QUALITATIVE):** To explore how playing a novel game affects people's choice of a spokesperson. Qualitative focus groups will be used to examine the group experience playing WWYC. One-on-one interviews will be used to explore how the game affected individual players' thought process for choosing a spokesperson, and whether that choice changed as a result of game-play.

**Aim 2 (QUANTITATIVE):** To establish that WWYC is a feasible way to help individuals choose and engage a spokesperson. We will judge WWYC as feasible if:

- We can efficiently recruit 100 individuals to play the game;
- $\geq 75\%$  of game players report that playing the game is helpful for choosing a spokesperson;
- $\geq 75\%$  of game players endorse the game, as measured by the Net Promoter Score;
- $\geq 75\%$  of spokespersons engage with WWYC (using its online interface) following player request

**Aim 3 (CONVERGENT MIXED METHODS):** To integrate qualitative and quantitative data via a joint display to explain how the experience of playing WWYC relates to their spokesperson's willingness to

engage. We hypothesize that positive player experience with WWYC will be associated with successful engagement with their spokesperson.

If successful, this study will establish the feasibility of a serious game for helping people choose a spokesperson for medical decision-making, and result in the creation a fully functional prototype (including its online interface). We will then be positioned to conduct a randomized controlled trial evaluating the efficacy of WWYC (compared to standard methods) for improving concordance between patients' wishes and spokespersons' decisions on their behalf.

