## 1.2 Primary Study Endpoints

Successful completion of data collection of 800 participants (400 players and 400 spokespersons) who play the "Who Would You Choose" game.

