## 1.3 Secondary Study Endpoints

Establish feasibility of game intervention

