## 7.0 Study Design and Procedures

## 7.1 Study Design

This study will use a convergent mixed methods design to: 1) explore how playing the serious game, “Who Would You Choose” (WWYC), affects individuals’ choice of a spokesperson; 2) establish the feasibility of using WWYC for helping people designate an appropriate spokesperson for healthcare decisions and 3) receive a positive response from the spokesperson which will be confirmed with a completed REDCap survey. In each game event (lasting ~2 hours), research staff will help facilitate game-play for groups of 4 players, who will also 1) complete baseline questionnaires, 2) complete post-game questionnaires, and 3) participate in post-game focus group discussions. Then, players will use text messages initiated by the associated WWYC smartphone App to engage their chosen spokespersons by sending a text message inviting them to complete a brief REDCap survey asking what medical preferences they think the player would want in various clinical scenarios. If this spokesperson does not respond or complete the survey within one week, the player may forward the same test message with REDCap survey link to an alternate spokesperson. If the alternate spokesperson does not respond or complete the survey, no additional spokespersons will be contacted. Approximately 2 weeks after the game event, players will be contacted by phone for a one-on-one interview.

Game piece examples:

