## 8 Subject Numbers and Statistical Plan

### 8.2 Number of Subjects

Up to 800 participants (400 players and 400 spokespersons, with each game consisting of 4 players each)

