### 8.3 Sample size determination

Using purposive sampling, aim to recruit 50% female and >25% ethnic/racial minority participants. As a feasibility study, the main objective is to establish viability of the intervention rather than efficacy. Thus a power analysis is not necessary. The sample size reflects the number of participants we expect to be able to recruit in this time period to obtain the information necessary to answer study questions.

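### The primary endpoint equals the enrolment ceiling and allows no loss, while Aim 2 counts recruitment as feasible at 100 players, so the study can pass every Aim 2 threshold and fail its primary endpoint

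*Combined protocol and SAP*

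**What the plan says.** Section 1.1, Aim 2, lists the conditions under which the game will be judged feasible. The first is "We can efficiently recruit 100 individuals to play the game". Two others require at least 75% of players to find the game useful and to endorse it. The fourth requires at least 75% "of spokespersons engage with WWYC (using its online interface) following player request".

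Section 1.2 gives the primary endpoint as "Successful completion of data collection of 800 participants (400 players and 400 spokespersons". Section 1.3 gives the secondary endpoint as "Establish feasibility of game intervention", with no number.

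Section 8.2 sets the number of subjects: "Up to 800 participants (400 players and 400 spokespersons, with each game consisting of 4 players each". Section 8.3 declines a power analysis and says "The sample size reflects the number of participants we expect to be able to recruit in this time period", again with no number. Section 4.2.3 gives the recruitment period as August 2021 to June 2023.

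Section 7.1 lets a player approach one alternate if the first spokesperson has not responded within a week, and then stops: "If the alternate spokesperson does not respond or complete the survey, no additional spokespersons will be contacted". One of the design objectives in that section is to "receive a positive response from the spokesperson which will be confirmed with a completed REDCap survey".

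Section 8.4 says that the primary outcome variables follow from criteria given earlier and will be summarised descriptively to see whether they reach the required feasibility levels.

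**The concern.** No significance testing is planned as a primary goal, so the pre-stated thresholds are in effect the study's whole decision rule. Two features of them need attention.

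First, the primary endpoint is set at the maximum number of people who may be enrolled. A single player who is not recruited or does not complete is enough to miss it.

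Second, Aim 2 can be passed far below that point, and the sections disagree about which standard is primary. A final count of 100 to 399 players would meet the numeric part of the first Aim 2 criterion and miss the primary endpoint. The report would then have to call the game feasible and the primary endpoint failed, with no sentence in the protocol explaining how the two results fit together. Section 1.1 makes success in this study the basis for a later randomised trial, so the recruitment conclusion should be unambiguous.

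**Working it through.** **Inputs.** Feasible recruitment: 100 players; engagement pass mark: at least 75% (Section 1.1, Aim 2). Primary endpoint: 400 players and 400 spokespersons with completed data (Section 1.2). Ceiling: the same 400 and 400 (Section 8.2). Invitations: one spokesperson plus at most one alternate per player (Section 7.1). The documents give no expected response or loss rate, so every rate below other than the 75% pass mark is an assumption.

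**The plan's own figure.** 400 + 400 = 800, which reproduces the stated total. No power formula applies.

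**Gap between the two standards.** 100 / 400 = 25%. The smallest study that meets the numeric parts of Aim 2 has 100 players and 0.75 × 100 = 75 spokespersons: 100 + 75 = 175, and 175 / 800 = 21.9%.

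**No room for player loss.** To obtain 400 completers with a loss fraction d, the study must enrol 400 / (1 − d), rounded up:

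| Assumed loss | Enrolment needed | Ceiling |
|---|---|---|
| 1% | 405 | 400 |
| 5% | 422 | 400 |
| 10% | 445 | 400 |
| 25% | 534 | 400 |

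Any positive loss from a full enrolment of 400 misses the endpoint.

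**The spokesperson half, for illustration.** Assume that engagement means a completed survey, that one spokesperson is counted per player, and that the realised rate is exactly the 75% pass mark. Without alternates, 400 players yield 0.75 × 400 = 300 spokespersons, a total of 700 of 800. If every one of the 100 remaining players then uses an alternate who responds with probability r, the count is 300 + 100r:

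| Assumed alternate response r | Spokespersons | Total of 800 |
|---|---|---|
| 0% | 300 | 700 |
| 50% | 350 | 750 |
| 75% | 375 | 775 |
| 100% | 400 | 800 |

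Only the last row reaches the endpoint. In the 75% row, 375 of 500 people contacted is 75%, so the fourth Aim 2 criterion is still just met on that denominator, whereas 375 of 400 players is 93.75%.

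**How high completion would have to be.** If each of 400 players independently yields a completed survey with probability p, the chance that all do is p^400: about 1 × 10⁻⁹ at p = 95%, 1.8% at p = 99%, and 67% at p = 99.9%.

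**Labels side by side.** Section 1.2 makes the 800 completers primary. Section 1.3 makes feasibility secondary. Section 8.4 treats as primary the outcomes compared with feasibility levels, and only the Aim 2 list contains such levels.

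**The case against.** The strongest reply is that 100, 400 and the ceiling answer different questions. Aim 2 sets a success threshold, Section 1.2 describes completion of data collection, and Section 8.2 caps enrolment. A floor can sit below a cap, so a reader who infers that 100 and 400 contradict each other goes too far. This stands. What is missing is a statement of the relation.

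A reader might also infer that the 75% criterion contradicts the 400-spokesperson target, or that the plan predicts its own failure. The documents do not support that. At least 75% is a pass mark, and nothing says it is the expected rate. The figures of 300 and 375 are scenarios.

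Two steps in those scenarios are assumptions. Section 7.1 ties survey completion to a positive response under a design objective; the protocol does not define engagement with the online interface that way. Nor does any section close the first link once an alternate is invited, so one player could in principle yield two completed surveys. The requirement that every player yield a spokesperson is therefore conditional. The requirement for all 400 players is not.

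It would also be too strong to say that nothing identifies the feasibility rule or the time frame. Aim 2 states the rule, the end of the Section 8.4 sentence points back to it, and Section 4.2.3 gives a recruitment window. The remaining faults are that the first criterion does not cite that window and that Sections 1.2 and 1.3 label the endpoints the other way round from Section 8.4.

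**Conclusion.** The point holds as a problem with how the primary endpoint is set and labelled. The endpoint can be met only with 400 completing players, which is the most that may be enrolled. On the assumption of one counted spokesperson per player, it also needs 100% spokesperson completion. Every numeric threshold in Aim 2 can be met at 22% of the 800 participants the endpoint needs. The documents neither say that 100 is a minimum within a cap of 400 nor give one consistent label to the feasibility criteria.

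The size is minor to moderate. No power figure, test or safety matter is affected, and the final count can be reported against both numbers. It is still worth correcting before the results are written up, because it changes which result counts as the study's primary finding.

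**What to change.** Do one of the following in Section 1.2:

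- make the Aim 2 criteria the primary endpoint, in line with Section 8.4, remove feasibility from Section 1.3, and leave 400 and 400 in Section 8.2 as the cap; or
- restate the endpoint as a player number below the cap, plus the percentage of players whose first or alternate spokesperson completes the survey. Section 8.4 should then say that this is the primary endpoint and that the Aim 2 criteria are secondary.

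In Section 1.1, state that 100 players is the minimum for feasibility within August 2021 to June 2023, with enrolment capped at 400 players, and give the reason for 100. Alternatively, use one player target throughout Sections 1.1, 1.2 and 8.2. Either way, define engagement and its denominator (spokespersons contacted or players), since the two can differ as shown above.

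The cost is a protocol amendment with no new data collection. The price is a stated primary endpoint that is less ambitious or, if a single player target above 100 is adopted, a recruitment criterion that is harder to meet. If the change comes after counts are known, it should be dated and the result reported against both the old and the new figures.

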### 2.2 Previous Data

Describe any relevant preliminary data.

We conducted feasibility and pilot testing of a revised WWYC game at 9 different venues with 93 participants (77% female, 25% minorities, see Table 3). Using a 10-point scale, we found that the majority of participants enjoyed playing the game (7.6 +/- 1.6), found it engaging (8.3 +/- 1.6), and would recommend it to others (7.3 +/- 2.3). More importantly, 84% (78/93) of participants reported that playing the game helped them “to think more deeply about the characteristics a healthcare spokesperson should have,” and 75% (70/93) said it prompted them “to think more deeply about who should be their own healthcare spokesperson.”

We refined the game by holding multiple informal game sessions to elicit feedback on game mechanics. Following modifications, we held formal game events using beta-versions of WWYC at 4 different venues (n=39 participants) with games facilitated by research to ensure rigor and fidelity. In post-game focus groups, players reported that playing WWYC was thought-provoking and enjoyable, and that it changed their views about choosing a spokesperson.

Table 3	GAME (Stage 1A)	GAME (Stage 1B)
Participants (n)	39	93
Female	9 (24%)	72 (77%)
Caucasian	18 (46%)	93 (75%)
Events (n)	4	9
Games (n)	8	18

staff

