The WWYC smart-phone App will supplement the cards, dice, and spinner to provide a secure dynamic database for up to 6 players at a time. Once the game question for a given round has been selected, and each player has typed a response using their smart-phone, the App will display all responses, and allow players to guess which player gave which response. The App will keep track of players' scores (reflecting the number of correct guesses), as well as point totals. Because the App is also intended to promote engagement with spokespersons, the App will allow players to invite their spokesperson to participate. Through the App, participants will share a link with their spokesperson via text message.

Research staff coordinating the game event will visually confirm participants have forwarded this survey to their potential spokesperson. By clicking the link, the spokesperson will view the Summary Explanation of Research, confirm willingness to participate, and provide basic demographic information through REDCap. Should this spokesperson not respond after seven days, the player may forward the survey invitation link to an alternative spokesperson. Should the alternate not respond, no additional invitations will be sent. Upon leaving the event, participants will be given a formal healthcare power of attorney form to complete. Additionally, ~2 weeks after the event, the research team will contact participants by phone to conduct follow-up interviews.

Post-Game Outcomes Measured:

- Experience/process of game-play (i.e., one-on-one interviews, focus groups)
- Net Promoter Score
- Stage of Readiness to Choose a Spokesperson
- Choosing a Spokesperson
- Spokespersons' Engagement with Online Interface
- Player Evaluation

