### 8.4 Statistical methods

**Quantitative data** will be analyzed by first summarizing all variables with frequencies and percentages, or means, standard deviations, medians, and quartiles. The primary outcome variables will then be defined based on criteria stated above and summarized with frequencies and percentages to determine

if they reach the needed feasibility levels. As a feasibility study, we are not performing statistical testing or seeking significance as a primary goal. All analyses will be performed using SAS version 9.4

**Qualitative data** will undergo conventional content analysis to identify emergent themes—with focus groups and 1:1 interviews analyzed separately. All inter-disciplinary team members will review 20% of transcripts independently to create broad categories. Categories and subcategories will then be organized into a preliminary codebook, and exemplars selected to further define the codes—which will then be used to code an additional 20% of transcripts using the constant comparison method.

**Biological variables** including age and gender will be assigned as attributes to examine effects on participant experiences. Inter-rater reliability will be judged using a kappa  $>0.7$ ; discrepancies will be managed by group discussion to arrive at consensus codebook for coding the entire dataset (2 coders per transcript). Experienced qualitative researchers ([name], [name]) will oversee analyses; coders will be trained by experienced members of the Penn State Qualitative Mixed Methods Core. Published criteria for **methodological rigor of qualitative research** will be used to attend to the truth-value, applicability, consistency, and neutrality of findings. To evaluate credibility (i.e., truth-value) of findings, a sub-set of participants will be asked to review a summary of data to ensure accuracy (member checking). To bolster applicability of findings to other contexts, rich/thick descriptions from interviews will be obtained to assess and compare experiences. Consistency and dependability of data will be maintained by inter-rater reliability analyses using intra-class correlation coefficients. Researchers will bracket biases and create an audit trail of coding decisions to maximize data neutrality.

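### Must the plan state which Net Promoter Score answer counts as endorsing the game before the 75% criterion in Aim 2 can be used?

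*Combined protocol and SAP*

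**What the plan says.** Section 1.1, Aim 2, lists four conditions for calling the game feasible. The third is that at least 75% "of game players endorse the game, as measured by the Net Promoter Score". The only other mention of the instrument is in the list of post-game outcomes in section 7.2, as a bare name: "Net Promoter Score".

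Section 8.4 says quantitative data "will be analyzed by first summarizing all variables with frequencies and percentages", or alternatively with means, standard deviations, medians and quartiles. It continues: "The primary outcome variables will then be defined based on criteria stated above". These outcomes are then summarised as frequencies and percentages and compared with the required levels. On inference, 8.4 says "we are not performing statistical testing or seeking significance as a primary goal".

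Section 2.2 reports an earlier pilot in 93 people. Two items are given as counts; one of them reads "and 75% (70/93) said it prompted them". The recommend item is given only as a mean and spread on a 10-point scale: "and would recommend it to others (7.3 +/- 2.3".

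**The concern.** A criterion with a numerical threshold needs a rule that sorts each player into yes or no. Here the threshold is stated but the rule is not: the document gives no question wording, response scale, qualifying score or treatment of players who leave the item blank. The name of the instrument adds some doubt, because a net score is a single figure for the group, whereas the criterion speaks of a percentage of players.

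The sequence in section 8.4 sharpens the worry. Read literally, everything is tabulated first and the outcomes are defined afterwards, so the qualifying score could be chosen once the distribution is known. With no testing planned, the verdict is an observed percentage set against 75%, and the definition carries all the weight. The same answers could be reported as meeting or missing the target. Section 1.1 treats success as the step towards a randomised trial.

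**Working it through.** The plan has no derived figure to reproduce; 75% is a chosen threshold. Two questions can be checked: how much the missing rule could matter, and what the plan already settles.

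**1. The cut-off, using the pilot item as a stand-in.** Inputs from section 2.2: n = 93, mean 7.3, spread 2.3. It is an assumption that this item matches the study item and that all 93 answered in whole numbers. The end points of the scale are not given, so both 1–10 and 0–10 were tried.

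- The spread must be an SD. Read as a standard error it would imply an SD of 2.3 × √93 = 22.2, while the largest possible SD at mean 7.3 is √(7.3 × 2.7) = 4.4 on 0–10, or √(6.3 × 2.7) = 4.1 on 1–10.
- Answers needed for 75%: 0.75 × 93 = 69.75, so 70.
- A mean that rounds to 7.3 puts the total between 675 and 683 (93 × 7.25 = 674.25; 93 × 7.35 = 683.55). An SD that rounds to 2.3 puts the sum of squared deviations between 92 × 2.25² = 465.75 and 92 × 2.35² = 508.07.

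An exact integer search over all sets of answers within these limits gives:

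| Counts as endorsing | Fewest–most of 93 (1–10) | Fewest–most of 93 (0–10) | 70 reached? |
|---|---|---|---|
| 9 or more | 3–61 | 0–61 | No |
| 8 or more | 24–83 | 22–85 | Undetermined |
| 7 or more | 34–85 | 34–87 | Undetermined |
| 6 or more | 46–90 | 46–90 | Undetermined |
| 5 or more | 62–93 | 62–93 | Undetermined |
| 4 or more | 73–93 | 73–93 | Yes |

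The two firm rows can be checked by hand with the one-sided Chebyshev (Cantelli) bound, SD²/(SD² + k²), using the least favourable rounding:

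- 9 or more: k = 9 − 7.35 = 1.65, so the share is at most 5.5225/(5.5225 + 2.7225) = 0.670, or 62 of 93, which is below 70.
- 3 or less: k = 7.25 − 3 = 4.25, so the share is at most 5.5225/(5.5225 + 18.0625) = 0.234, or 21 of 93. At least 72 therefore score 4 or more.

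With smooth shapes assumed for the same mean and SD, 78–79% score 6 or more and 64–68% score 7 or more, so the verdict would turn between those two cut-offs.

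**2. Blank answers.** Assume 10% blank. With 100 players, the fewest endorsers that reach 75% of those who answered is 68: 68/90 = 75.6%, but 68/100 = 68%. With 400 players, 270/360 = 75.0%, but 270/400 = 67.5%.

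**3. What the plan settles.**

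- *Share or net score.* Aim 2 speaks of a percentage of players, and 8.4 summarises outcomes as frequencies and percentages. Both point to a share.
- *Item and scale.* These are fixed by the questionnaire the players fill in, so they cannot be chosen after the answers are seen.
- *Threshold.* Section 8.4 ties the definitions to criteria already stated, and those contain the 75%. The ordinary reading is a workflow: describe the data, then derive the yes/no variables.
- *Blanks.* Section 7.1 has players complete the post-game questionnaires at the facilitated event, which should keep blanks few; the 10% above is only illustrative.
- *Visibility.* Under 8.4 the score is summarised by frequencies or by quartiles. Frequencies show the share at every cut-off. The lower quartile is the score that about three quarters of respondents reach or exceed, so a cut-off at or below it meets 75% and one above it does not, apart from the boundary case of exactly 75%. The planned summary therefore shows whether the verdict depends on the cut-off.

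**The case for a change.** The strongest case for a change is that one sentence would close the gap at almost no cost. The cut-off decides the verdict over a plausible range, and a reader cannot confirm from the document that it was chosen before the data were seen. Calling the study a feasibility study does not excuse this, because the feasibility verdict is what the criteria deliver. If a strict cut-off of 9 is intended, the pilot item could not have met 75%, which suggests the target was not checked against the pilot.

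Much of this stands as description. The qualifying score and the rule for blanks are indeed unwritten, and recording them beforehand would be tidy. The rest is weaker. The pilot argument needs an unstated link: section 2.2 never calls its recommend item a Net Promoter Score, and it concerns an earlier version of the game. The ordering argument depends on reading 8.4 without its reference back to the stated criteria. The proposed sentence would also leave the choice of cut-off to the investigators, so it adds documentation without correcting a method.

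**Conclusion.** No change to the plan is needed. The detail is missing, but no stated rule is wrong and the ordinary reading of section 8.4 does not produce a wrong result. The threshold is set, the text points to a share of players, and the form fixes the item and scale. Only the qualifying score and the treatment of blanks are left to the analysts, who can settle both sensibly.

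The possible effect is real but bounded. On the pilot figures the verdict is open only for cut-offs of 5 to 8; it is a certain miss at 9 or above and a certain pass at 4 or below. That rests on the pilot item standing in for the study item, on whole-number answers from all 93, and on 2.3 being an SD. The blank-answer example rests on an assumed 10%. The matter touches one of four descriptive criteria, involves no test or error rate, and will be visible in the frequencies or quartiles already planned if these are reported with the result.
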